9.3. Adverse Events

When calculating the incidence of adverse events (i.e., on a per subject basis), each subject will only be counted once and any repetitions of adverse events within a subject will be ignored; the denominator will be the total safety population size and population within actual treatment group. All adverse events reported will be included in the summaries and analyses. All analyses in Section 9.3 will be performed in the safety analysis population using the actual treatment received.

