9.3.1. Solicited Events and Symptoms

Solicited urogenital symptoms were collected before study product administration, and then daily for 5 days and graded on a scale of 0 (absent), 1 (mild), 2 (moderate) and 3 (severe). Urogenital symptoms include: vaginal odor, vaginal pain, vaginal tenderness, vulvar/vaginal itching, vaginal dryness, vaginal discharge, and vulvar inflammation. Any symptom that is present at the time that the subject is screened should be considered as baseline and not reported as a solicited urogenital AE. However, if it deteriorates at any time during the study, it will be recorded as a solicited urogenital AE. If a symptom is reported that was not present at baseline, it too will be recorded as a solicited urogenital AE. Treatment emergent solicited urogenital adverse events will be identified by comparing the severity of the baseline solicited urogenital symptoms with the severity of the post-baseline solicited urogenital symptoms. If the severity increases post-baseline or the symptoms appears post-baseline when it was 'None' at baseline, then the symptom will be considered to be treatment-emergent.

The first primary safety endpoint is the number of subjects reporting treatment-emergent solicited urogenital AEs following the first dose of the study product through Visit 2 (Day 8-15).

The number and percent of subjects reporting at least one treatment-emergent solicited urogenital adverse event will be summarized for each solicited adverse event and any solicited adverse event along with the 95% Clopper-Pearson CI and presented in **Table 62**. **Table 63** will present the proportion of subjects experiencing any solicited urogenital event and each specific urogential solicited event, along with the 95% Clopper-Pearson CI of the proportion, the difference in the proportions of subjects experiencing a solicited event between 5% Monolaurin Vaginal Gel and Placebo Gel, the 95% Exact CI of the difference and the p-value for a Fisher's exact test. A Fisher's exact test will be performed to test for the difference in the proportion of subjects reporting a treatment emergent solicited urogenital adverse event. The null hypothesis is that there is no difference in proportions of subjects reporting solicited urogenital AEs between treatment groups, with a two-sided alternative which considers the possibility of a difference in either direction. Section 6.1 provides pseudo SAS code to use for the analyses.

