For each treatment-emergent solicited urogenital adverse event and any solicited adverse events, the maximum severity over 5 days after the first dose will be summarized for the Safety population. The number and percentage of subjects reporting each treatment-emergent solicited adverse event will be summarized by the maximum severity and actual treatment group along with the 95% Clopper-Pearson CIs. For each event the denominator is the number of subjects with non-missing data for the specific solicited urogenital adverse event. See **Table 64** and **Figure 6**.

Table 64 and **Figure 7** will summarize any reported solicited symptom (treatment-emergent and non treatment-emergent) and each solicited symptom by maximum severity over 5 days after the first dose along with the 95% Clopper-Pearson CI for the Safety population. The number and percentage of subjects reporting each symptom will be summarized by the maximum severity and actual treatment group. For each event, the denominator is the number of subjects with non-missing data for the specific symptom. Maximum severity of solicited symptoms is displayed by study day and treatment group in **Figure 8**.

The number of subjects reporting a solicited symptom will be summarized for each day for all subjects and separately for each treatment group (**Tables 66-68**) and graphically in a bar chart (**Figure 7**).

Solicited symptoms by subject will be presented in Listing 12.

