	None	х	х	X,X	х	x	x,x	х	х	X,X	
	Mild	х	х	x,x	х	x	x,x	х	х	X,X	
Vaginal Discharge	Moderate	х	х	X,X	х	x	x,x	х	х	X,X	
	Not Reported	х	х	X,X	х	x	x,x	х	х	X,X	
	Total	х	х	X,X	х	x	x,x	x	х	X,X	
	None	х	х	x,x	х	x	x,x	х	х	X,X	
	Mild	х	х	X,X	х	х	x,x	х	х	X,X	
	Moderate	х	х	X,X	х	х	X,X	х	х	X,X	
Vulvar Inflammation	Severe	х	х	X,X	x	х	x,x	х	х	X,X	
	Not Reported	х	х	X,X	х	х	X,X	х	х	X,X	
	Total	х	х	x,x	х	x	x,x	х	х	X,X	

Table 65 Number and Percentage of Subjects Experiencing Solicited Symptoms by Symptom, Maximum Severity, and Treatment Group-Safety Population (continued)

 I total
 x
 x
 x,x
 x
 x,x
 x
 x,x
 x
 x,x

 Notes: Denominator for percentages is the number of subjects in the Safety Population (N) with solicited symptom data available for the specific symptom for each treatment group.

 1Each subject's maximum severity is reported for each solicited symptom across all doses. Table includes solicited symptoms reported from the first dose of study product through Visit 2.

		Pre- (N	-Dose =X)	Da (N	iy 1 =X)	Da (N	ay 2 =X)	Da (N	iy 3 =X)	Da (N	ny 4 =X)	Da (N=	iy 5 =X)
Solicited Symptom	Severity ¹	n	%	n	%	n	%	n	%	n	%	n	%
Any Solicited Symptom	None	х	x	х	х	х	x	x	х	Х	х	x	X
	Mild	х	x	х	х	х	x	х	х	х	х	x	x
	Moderate	х	x	х	х	х	x	x	х	Х	х	x	X
	Severe	х	х	х	х	х	х	х	x	х	x	х	Х
	Not Reported	х	x	х	х	х	x	x	х	Х	х	x	X
	Total	х	x	х	х	х	x	x	х	Х	х	x	X
Vaginal Odor	None	х	x	х	х	х	x	х	х	х	х	x	x
	Mild	х	x	х	х	х	x	x	х	Х	х	x	X
	Moderate	х	х	х	х	х	х	х	x	х	x	х	Х
	Severe	х	х	х	х	х	х	х	x	х	x	х	Х
	Not Reported	х	x	х	х	х	x	х	х	х	х	x	x
	Total	х	х	х	х	х	х	х	x	х	x	х	Х
Vaginal Pain	None	х	x	х	х	х	x	х	х	х	х	x	x
	Mild	х	x	х	х	х	x	х	х	х	х	x	X
	Moderate	х	x	х	х	х	x	х	х	х	х	x	x
	Severe	x	x	х	x	x	x	x	x	x	х	x	x
	Not Reported	х	x	х	х	х	x	x	х	Х	х	x	X
	Total	х	x	х	х	х	x	x	х	Х	х	x	X
Vaginal Tenderness	None	x	x	х	x	x	x	x	x	x	х	x	x
	Mild	x	x	х	x	x	x	x	x	x	х	x	x
	Moderate	х	x	х	x	x	x	x	x	х	х	х	х
	Severe	x	x	х	x	x	x	x	x	x	х	x	x
	Not Reported	х	x	x	х	х	x	x	x	х	x	x	х
	Total	х	х	х	х	х	х	х	х	х	х	х	x

Table 66:Number and Percentage of Subjects Experiencing Solicited Symptoms by Symptom, Severity, Study Day, and
Treatment Group - All Treatment Groups - Safety Population

Statistical Analysis Plan DMID Protocol 12-0021

		Pre- (N	-Dose =X)	Da (N	ay 1 =X)	Da (N	ny 2 =X)	Da (N	ny 3 =X)	Da (N=	y 4 =X)	Da (N=	y 5 =X)
Solicited Symptom	Severity ¹	n	%	n	%	n	%	n	%	n	%	n	%
Vulvar/Vaginal Itching	None	х	х	x	х	x	х	х	х	x	х	x	x
	Mild	х	х	x	х	x	х	х	х	x	х	x	x
	Moderate	х	х	x	x	x	Х	х	х	x	х	x	x
	Severe	х	х	x	х	x	х	х	х	x	х	x	x

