	Not Reported	x	х	х	х	x	х	х	х	x	x	x	x
	Total	х	х	x	х	x	х	х	х	x	х	x	x
Vaginal Dryness	None	х	х	x	х	x	х	х	Х	х	х	x	x
	Mild	х	х	x	х	х	х	х	х	х	х	х	х
	Moderate	х	х	x	х	x	х	х	Х	х	х	x	x
	Not Reported	х	х	х	х	x	х	х	Х	х	х	x	x
	Total	х	х	x	х	x	х	х	Х	х	х	x	x
Vaginal Discharge	None	х	х	x	х	x	х	х	Х	х	х	x	x
	Mild	х	х	х	х	x	х	х	х	х	x	х	х
	Moderate	x	х	х	x	x	х	х	х	x	x	x	x
	Not Reported	х	х	х	х	x	х	х	Х	х	х	x	х
	Total	x	х	х	x	x	х	х	х	x	x	x	x
Vulvar Inflammation	None	x	х	х	x	x	х	х	х	x	x	x	x
	Mild	х	х	x	x	х	х	x	х	х	х	x	х
	Moderate	x	х	х	x	x	х	х	х	x	x	x	x
	Severe	х	х	x	х	x	х	х	Х	х	х	x	x
	Not Reported	х	X	X	x	х	x	x	X	x	х	x	х
	Total	х	х	х	x	х	х	x	х	x	х	х	х

Table 66 Number and Percentage of Subjects Experiencing Solicited Symptoms by Symptom, Severity, Study Day, and Treatment Group-All Treatment Groups - Safety Population (continued)

Notes: Denominator for percentages is the number of subjects in the Safety Population (N) with solicited event data available reporting a solicited adverse event at the day being summarized for each treatment group.

¹The maximum severity of any solicited adverse event is summarized. A subject is only counted once at the maximum severity.

- Table 67:Number and Percentage of Subjects Experiencing Solicited Symptoms by Symptom, Severity, Study Day, and
Treatment Group-5% Monolaurin Vaginal Gel Safety Population
- Table 68:Number and Percentage of Subjects Experiencing Solicited Symptoms by Symptom, Severity, Study Day, and
Treatment Group-Placebo Gel Safety Population

Table 69:Proportion of Subjects Reporting Non-Solicited Non-Laboratory Adverse Events Following the First Dose of
Study Product through Visit 3 by Treatment Group - Safety Population

Treatment Group	Number of Subjects with AEs n	Number of Subjects N	Proportion of Subjects with AEs	Proportion of Subjects with AEs 95% CI	Difference in Proportion of Subjects with AEs between 5% Monolaurin Vaginal Gel and Placebo Gel	Difference in Proportion of Subjects with AEs between 5% Monolaurin Vaginal Gel and Placebo Gel 95% CI
5% Monolaurin Vaginal Gel	х	х	0.xx	0.xx, 0.xx	0.xx	0.xx, 0.xx
Placebo Gel	х	х	0.xx	0.xx, 0.xx		
All Subjects	x	x	0.xx	0.xx, 0.xx		

Table 70:Number and Percentage of Subjects Experiencing Non-Solicited Non-Laboratory Events with 95% Confidence
Intervals by MedDRA System Organ Class, and Preferred Term, and Treatment Group - Safety Population

		5% Mono	laurin V (N=X)	Vaginal Gel		Placeb (N=	o Gel X)	All Subjects (N=X)			

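### SAP Tables 66-68 take daily symptom percentages over only the women who reported an event that day, so the percentage columns cannot be compared between arms

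*SAP*

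**What the plan says.** SAP Section 9.3.1 introduces the daily tables with one sentence: "The number of subjects reporting a solicited symptom will be summarized for each day for all subjects and separately for each treatment group". It gives them no denominator. The shell of Table 66 has columns for Pre-Dose and Days 1 to 5, each with n and %. Each symptom block has rows for None, the severity grades, Not Reported and Total. Tables 67 and 68 repeat the format for the active and placebo arms.

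The only denominator rule specific to these tables is the Table 66 footnote: "Denominator for percentages is the number of subjects in the Safety Population (N) with solicited event data available reporting a solicited adverse event", followed by "at the day being summarized for each treatment group". To enter the denominator a woman must have data and must also have reported an event that day.

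Other rules in the same part of the SAP carry no such condition:

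- Table 65, on the same symptoms: "Denominator for percentages is the number of subjects in the Safety Population (N) with solicited symptom data available for the specific symptom".
- Section 9.3.1, on maximum severity of any reported symptom: "For each event, the denominator is the number of subjects with non-missing data for the specific symptom". The text cites Table 64 here, but the description is that of Table 65.
- Section 9.3, on adverse event incidence generally: "the denominator will be the total safety population size and population within actual treatment group".

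**The concern.** A percentage of women with a symptom needs a base that includes women without one. The footnote removes them from the base, while the shell keeps a None row in which to count them. Numerator and denominator then describe different groups.

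At stake is the daily course of solicited symptoms by arm, which among the planned tables only Tables 66-68 give. A reader comparing the percentage columns of Tables 67 and 68 would see figures driven by the base and not by how often symptoms occurred. The base also shrinks by a different factor in each arm when reporting rates differ.

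**Working it through.** The shells hold only placeholders, so there is no plan figure to reproduce. The check is algebra on the footnote, followed by an illustration.

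**Inputs.** SAP Section 4.1 gives 120 women allocated 2:1, hence 80 and 40. Assumed: all are dosed and all have diary data on the day. The documents give no daily symptom rate, so rates from 10% to 80% are assumed.

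**Notation.** D = women with data that day; E = women reporting an event that day.

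**Formulas, any-symptom block.**

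- Footnote base: Mild + Moderate + Severe = E/E = 100% for every E of at least 1. None = (D − E)/E, which exceeds 100% exactly when E < D/2.
- Base of women with data: Mild + Moderate + Severe = E/D. None = (D − E)/D.

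| Arm | D | E | Any symptom, footnote | None, footnote | Any symptom, base D | None, base D |
|---|---|---|---|---|---|---|
| Active | 80 | 24 | 24/24 = 100% | 56/24 = 233% | 30% | 70% |
| Placebo | 40 | 6 | 6/6 = 100% | 34/6 = 567% | 15% | 85% |
| Active | 80 | 40 | 40/40 = 100% | 40/40 = 100% | 50% | 50% |
| Placebo | 40 | 8 | 8/8 = 100% | 32/8 = 400% | 20% | 80% |

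Across symptom rates of 10%, 20%, 30%, 50%, 60% and 80%, None under the footnote is 900%, 400%, 233%, 100%, 67% and 25%.

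**Inflation of each row.** The factor is D/E: 80/24 = 3.3 in the active arm and 40/6 = 6.7 in the placebo arm in the first pair.

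**A single symptom.** Suppose 10 women have odor, 40 report some event, and 80 have data. The footnote prints 10/40 = 25% where 10/80 = 12.5% is meant, and None for odor prints as 70/40 = 175%.

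**Alternative readings.**

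- *Adverse event means treatment-emergent only.* On what counts as an adverse event, Section 9.3.1 says "Any symptom that is present at the time that the subject is screened should be considered as baseline and not reported as a solicited urogenital", with worsening as the exception. Tables 66-68 count all symptoms, so with S symptomatic and T treatment-emergent women (T no larger than S) the sum is S/T. With S = 60, T = 60 gives 100%, T = 40 gives 150% and T = 20 gives 300%. Nothing is treatment-emergent before dosing, so the Pre-Dose column divides by zero.
- *Numerators are also limited to reporters.* None in the any-symptom block is then 0% on every day.

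None of these readings gives a usable daily percentage.

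**The case against.** The case against giving this much weight is substantial, and most of it stands.

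- **The daily rates can be recovered.** A reader might infer that these tables cannot show whether symptoms are more common on active gel. The documents do not support that. Every row prints n, and None + Mild + Moderate + Severe gives the women with data. In the first example, 56 + 24 = 80 and 24/80 = 30%. Only the % column is spoiled.
- **There are other daily displays.** Section 9.3.1 assigns maximum severity by study day and arm to Figure 8. Listing 12 gives each woman's daily severities and stars the treatment-emergent ones. The footnote is attached to neither, although Figure 8 is not shown in the text, so its scale cannot be checked.
- **The primary safety outcome is untouched.** A reader might infer otherwise because the symptoms are the same. That outcome counts women with treatment-emergent events through Visit 2, and it is reported in Tables 62 and 63 with the Fisher test. Tables 66-68 are descriptive, cover all symptoms and include a pre-dose column.
- **An unconditional 100% goes too far.** No row carries an any-symptom percentage; it is the sum of three rows. It equals 100% only on days with at least one reporter, and only if adverse event means any symptom, as note 1 to Table 66 uses it.
- **The wording is probably an editing remnant.** Two phrases appear to have been run together, and a programmer would likely notice a None row above 100%.

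The last point does not dispose of the matter. No other text in the SAP overrides the footnote, and a programmer who noticed could choose either the non-missing base of Section 9.3.1 or the whole safety population of Section 9.3.

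**Conclusion.** The footnote is wrong as written and inconsistent with Table 65 and Section 9.3.1. The percentage columns of Tables 66-68 would not be comparable between arms under any literal reading. The algebra holds at any symptom rate. The sizes shown (30% against 15% printing as 100% against 100%; None at 233% and 567%) rest on the assumed 80/40 split, complete diaries and assumed rates.

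The reach is narrow: one percentage column per day in three descriptive tables. No count, confidence interval, endpoint or test changes. It is worth correcting because the correction is trivial and the tables would otherwise print figures that mislead or make no sense.

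**What to change.** In the Table 66 footnote, delete the five words after 'available' in the quoted text, which impose the reporting condition, and align the rest with Table 65. The footnote would then read: "Denominator for percentages is the number of subjects in the Safety Population (N) with solicited symptom data available for the specific symptom" (for the any-symptom block, for at least one symptom) "at the day being summarized for each treatment group". The parenthesis is needed because a base tied to one symptom leaves the any-symptom block undefined. Tables 67 and 68 follow the same format and need no separate text.

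Showing Not Reported as a count without a percentage is optional. Table 65 also shows it with a percentage, so any such change should be made in both places or in neither.

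The cost is one footnote in the table shells. It needs no new data and no change to study conduct or to any test.

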# 3.2. Study Outcome Measures

# 3.2.1. Safety Outcomes

All safety outcomes will be assessed in the safety analysis population of all subjects who received one or more doses of study product. Outcomes will be reported by treatment arm.

- Primary Safety Outcome
  - Number of subjects reporting solicited urogenital AEs following the first dose of the study product through Visit 2 (Day 8-15).
  - Number of subjects reporting serious adverse events (SAEs) considered product-related following the first dose of the study product through Visit 3 (Day 22-31)
- Secondary Safety Outcomes
  - Number of subjects experiencing non-laboratory non-solicited AEs following the first dose of the study product through Visit 3 (Day 22-31).

• Number of subjects experiencing laboratory AEs following the first dose of the study product through Visit 2 (Day 8-15).

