9.6. Clinical Laboratory Evaluations

Safety clinical laboratory data includes: WBC count, hemoglobin, platelets, neutrophil count, creatinine, AST (SGOT), ALT (SGPT), total bilirubin, and glucose (random). These hematology and chemistry parameters will be collected at Visit 1 and Visit 2. Laboratory abnormalities that were stable at Visit 2 will not be repeated at Visit 3. Laboratory abnormalities that occurred between Visit 1 and Visit 2 or worsened at Visit 2 will be repeated at Visit 3. A laboratory abnormality is considered an adverse event if there is a worsening of the laboratory value at Visit 2 from the baseline value and it increases in laboratory toxicity grading from the baseline toxicity grading. For laboratory abnormalities repeated at Visit 3, if there is a worsening of the laboratory toxicity grading, it is considered an additional adverse event. Toxicity grading can be found in Appendix B of the protocol. All analyses in Section 9.6 will be performed in the safety analysis population.

The second secondary safety endpoint is number of subjects experiencing laboratory AEs following the first dose of the study product through Visit 2 (Day 8-15). The number of subjects reporting at least one laboratory measurement at the visit, the proportion of subjects who experienced laboratory AEs, and the 95% Clopper-Pearson confidence interval for the proportion of subjects who experienced laboratory AEs will be presented by treatment group. In addition, the difference in proportions between the 5% Monolaurin Vaginal Gel arm and the Placebo gel arm and 95% Exact confidence intervals will be presented in **Table 89**.

The proportion of subjects with laboratory results meeting toxicity grading criteria will be presented for each parameter in **Tables 90 and 92** by severity, study day and treatment group. The proportion of subjects with laboratory results related to study product meeting toxicity grading criteria will be presented for each parameter in **Tables 91 and 93** by severity, study day and treatment group. Descriptive statistics including mean, standard deviation, median, mean change from baseline and associated standard deviation by study day, for each laboratory parameter, will be summarized in **Table 94** by treatment group. Laboratory values will be presented by parameter, severity and visit in **Figures 17-19**. Mean changes in laboratory values will be presented in **Figures 20-28**.

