The denominator for proportions is the number of subjects with each specific laboratory value at the visit.

Laboratory abnormalities are those that meet toxicity grading. When the site-specific laboratory normal range is available, if there is a discrepancy between the laboratory value in Appendix B of the protocol and the site-specific laboratory normal range, the value in Appendix B of the protocol will take precedence in determining Grade 1 adverse events. Otherwise, all laboratory tests will be graded per the toxicity table in Appendix B of the protocol. Unscheduled or repeated follow-up laboratory tests for medical or safety reasons will be listed, but excluded from tabular and graphical summaries.

A listing of laboratory tests with toxicity Grade ≥ 1 will also be provided. If a subject meets this criterion, the listing will provide data from all visits for the particular lab test that meet the criteria

so that the time course for the particular lab parameter can be observed. See **Tables 95-96.** A listing of all clinical laboratory values will be generated in **Listings 14 and 15.**

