		5	5% Monolaurin Vaginal Gel (N=X)						Placel (N=	bo Gel =X)					All Su (N⁼	bjects =X)			
		Vis Da (N=	sit 1 iy 1 =X)	Vis Da (N=	sit 2 1y 8 =X)	Vis Da (N	it 3* y 28 =X)	Vis Da (N⁼	sit 1 y 1 =X)	Vis Da (N=	iit 2 y 8 =X)	Vis Da (N	it 3* y 28 =X)	Vis Da (N=	sit 1 1y 1 =X)	Vis Da (N⁼	iit 2 y 8 =X)	Visi Day (N=	it 3* v 28 =X)
Laboratory Parameter	Severity	n	% n %		n	%	n	%	n	%	n	%	n	%	n	%	n	%	
	None	х	х	х	x	x	х	х	х	х	x	x	x	х	х	х	х	x	х
White Blood Cell Count, Increased	Any	х	х	х	x	x	x	х	х	x	х	x	x	х	х	х	х	х	х
	Mild	х	х	х	x	x	x	х	х	x	х	x	x	х	х	х	х	х	х
	Moderate	х	х	х	x	x	x	х	х	x	х	x	x	х	х	х	х	х	х
	Severe	х	х	х	x	x	x	х	х	x	х	x	x	х	х	х	х	х	х
	None	х	х	х	х	х	х	х	х	х	х	х	х	х	х	Х	х	х	х
	Any	х	х	х	х	х	х	х	х	х	х	х	х	х	х	х	х	х	х
Max of Hematology Parameters	Mild	х	х	х	x	x	x	х	х	х	x	x	x	х	х	х	х	x	х
	Moderate	х	х	х	х	х	х	х	х	х	х	х	х	х	х	х	х	х	х
	Severe	х	х	х	х	х	х	х	х	х	х	х	х	х	х	х	х	х	х

Table 90 Laboratory Results by Parameter, Maximum Severity, Study Visit, and Treatment Group- Hematology - Safety Population (continued)

Notes: N=number of subjects in the Safety Population reporting at least one laboratory measurement at the visit. Denominator for percentages is the number of subjects with the specific laboratory value at the visit.

*Laboratory abnormalities that were stable at Visit 2 will not be repeated at Visit 3. Laboratory abnormalities that occurred between Visit 1 and Visit 2 or worsened at Visit 2 will be repeated at Visit 3.

A laboratory abnormality is considered an adverse event if there is a worsening of the laboratory value from the baseline value and it meets the laboratory toxicity grading.

Tables with Similar Format:

Table 91:Laboratory Results Related to Study Product by Parameter, Maximum Severity, Study Visit, and Treatment
Group - Hematology - Safety Population

		5% Monolaurin Vaginal Gel (N=X)							Place (N	bo Gel =X)					All Th (N	erapie =X)	8		
		Vi Da (N	sit 1 ay 1 =X)	Vi Da (N	sit 2 ay 8 =X)	Vis Da (N	it 3* y 28 =X)	Vis Da (N	sit 1 ny 1 =X)	Vi Da (N	sit 2 1y 8 =X)	Vis Da (N	it 3* y 28 =X)	Vis Da (N=	sit 1 1y 1 =X)	Vi Da (N	sit 2 ay 8 =X)	Vis Day (N=	it 3* y 28 =X)
Laboratory Parameter	Severity	n	%	n	%	n	%	n	%	n	%	n	%	n	%	n	%	n	%
	None	х	х	х	х	х	х	х	х	х	х	х	х	х	х	х	x	х	x
	Any	х	х	х	x	х	х	х	х	х	x	х	х	x	x	x	x	х	х
Alanine Aminotransferase	Mild	х	x	x	х	х	х	х	х	х	x	х	х	х	x	х	x	х	x
	Moderate	х	х	х	х	х	х	х	х	х	x	х	х	х	x	х	x	х	х
Severe	Severe	х	х	х	х	х	х	х	х	х	х	х	х	х	х	х	x	х	х
	None	х	х	х	х	х	х	х	х	х	х	х	х	х	х	х	x	х	х

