(U/L)	Median	X.X	X.X	X.X	X.X	X.X	X.X	X.X	x.x	X.X
	Mean Change from Visit 1	-	X.X	X.X	-	X.X	X.X	-	x.x	X.X
	Standard Deviation	-	X.X	X.X	-	X.X	X.X	-	X.X	X.X
	n	х	х	х	х	х	х	х	х	X
	Mean	X.X	X.X	X.X	X.X	X.X	X.X	X.X	X.X	X.X
Aspartate	Standard Deviation	X.X	X.X	X.X	X.X	X.X	X.X	X.X	X.X	X.X
Aminotransferase (U/L)	Median	X.X	X.X	X.X	X.X	X.X	X.X	X.X	X.X	X.X
	Mean Change from Visit 1	-	X.X	X.X	-	X.X	X.X	-	X.X	X.X
	Standard Deviation	-	X.X	X.X	-	X.X	X.X	-	X.X	X.X
	n	х	х	х	х	х	х	х	х	X
	Mean	X.X	X.X	X.X	X.X	X.X	X.X	X.X	X.X	X.X
Dilin Lin (ma / JI)	Standard Deviation	X.X	X.X	X.X	X.X	X.X	X.X	X.X	X.X	X.X
Bilirubin (mg/dL)	Median	X.X	X.X	X.X	X.X	X.X	X.X	X.X	X.X	X.X
	Mean Change from Visit 1	-	X.X	X.X	-	X.X	X.X	-	X.X	X.X
	Standard Deviation	-	X.X	X.X	-	X.X	X.X	-	X.X	X.X
	n	х	х	х	х	x	x	х	х	x
Creatinine (mg/dL)	Mean	X.X	X.X	X.X	X.X	X.X	X.X	X.X	X.X	X.X
	Standard Deviation	X.X	X.X	X.X	X.X	X.X	X.X	X.X	X.X	X.X

Table 94 Laboratory Summary Statistics by Parameter, Study Visit, and Treatment Group - Safety Population (continued)

		5% Mo	nolaurin Vag (N=X)	ginal Gel		Placebo Gel (N=X)			All Subjects (N=X)	
Laboratory Parameter (unit)	Statistic	Visit 1 Day 1 (N=X)	Visit 2 Day 8 (N=X)	Visit 3 ¹ Day 28 (N=X)	Visit 1 Day 1 (N=X)	Visit 2 Day 8 (N=X)	Visit 3 ¹ Day 28 (N=X)	Visit 1 Day 1 (N=X)	Visit 2 Day 8 (N=X)	Visit 3 ¹ Day 28 (N=X)
	Median	X.X	X.X	X.X	X.X	X.X	X.X	X.X	X.X	X.X
	Mean Change from Visit 1	-	X.X	X.X	-	X.X	X.X	-	X.X	X.X
	Standard Deviation	-	X.X	X.X	-	X.X	X.X	-	X.X	X.X
	n	х	х	х	х	х	х	х	х	х
	Mean	X.X	X.X	X.X	X.X	X.X	X.X	X.X	X.X	X.X
Chucasa (mg/dL)	Standard Deviation	X.X	X.X	X.X	X.X	X.X	X.X	X.X	X.X	X.X
Glucose (mg/dL)	Median	X.X	X.X	X.X	X.X	X.X	X.X	X.X	X.X	X.X
	Mean Change from Visit 1	-	X.X	X.X	-	X.X	X.X	-	X.X	X.X
	Standard Deviation	-	X.X	X.X	-	X.X	X.X	-	X.X	X.X

Table 94 Laboratory Summary Statistics by Parameter, Study Visit, and Treatment Group - Safety Population (continued)

Notes: N = number of subjects in the Safety Population completing each visit;

n = number of subjects with a laboratory test at the visit specified.

¹Laboratory abnormalities that were stable at Visit 2 will not be repeated at Visit 3. Laboratory abnormalities that occurred between Visit 1 and Visit 2 or worsened at Visit 2 will be repeated at Visit 3. A laboratory abnormality is considered an adverse event if there is a worsening of the laboratory value from the baseline value and it meets the laboratory toxicity grading.

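### Visit 3 laboratory percentages and mean changes in SAP Tables 90-94 come only from women retested for a new or worse abnormality, so they cannot be read beside Visits 1 and 2

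*SAP*

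**What the plan says.** **Timing of draws.** SAP 9.6 schedules safety bloods twice: "These hematology and chemistry parameters will be collected at Visit 1 and Visit 2". Visit 3 is conditional. The same section says "Laboratory abnormalities that were stable at Visit 2 will not be repeated at Visit 3", and the footnotes to Tables 90, 92 and 94 add "Laboratory abnormalities that occurred between Visit 1 and Visit 2 or worsened at Visit 2 will be repeated at Visit 3". Protocol 7.3 and the Schedule of Events carry the same rule.

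**Tables.** Tables 90 and 92, and their product-related versions 91 and 93, have a Visit 3 column with n and % for each grade. The footnote reads "Denominator for percentages is the number of subjects with the specific laboratory value at the visit", and the text of SAP 9.6 agrees: "The denominator for proportions is the number of subjects with each specific laboratory value at the visit". Table 94 has Visit 3 columns for mean, standard deviation, median and mean change from Visit 1, with "n = number of subjects with a laboratory test at the visit specified".

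**Exclusion.** SAP 9.6 also says: "Unscheduled or repeated follow-up laboratory tests for medical or safety reasons will be listed, but excluded from tabular and graphical summaries".

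**Outcome.** The secondary outcome in Protocol 3.2.1 and SAP 3.2.5 is "Number of subjects experiencing laboratory AEs following the first dose of the study product through Visit 2 (Day 8-15"). SAP 4.5 and 9.6 decide whether an abnormality is an AE by comparing the Visit 2 value and grade with baseline. Table 89 reports the result.

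**The concern.** The columns for Visits 1 and 2 describe essentially everyone tested at those visits. The Visit 3 column describes women who needed a repeat. All three sit side by side under the same headings, and a reader will compare them as if they showed a time course. A percentage among retested women estimates how often a Visit 2 abnormality persists, not how common abnormality is at Day 28. Likewise, a mean change from Visit 1 among women selected for a shift between Visits 1 and 2 is not zero even when nothing happens in the trial population. What is at stake is the descriptive laboratory safety record.

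Two related points concern wording. The Visit 3 draws are repeats made to follow up an abnormality, so the exclusion sentence, read literally, empties the columns that the shells require. Separately, the outcome covers the whole period from first dose through Visit 2, but the rule looks only at the Visit 2 value. A graded worsening seen on an unscheduled draw and gone by Visit 2 would appear in listings but not in Table 89.

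**Working it through.** The plan states no laboratory abnormality rate, so there is no figure of its own to reproduce. The size is shown on assumed inputs.

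**1. Denominators.** Inputs from the documents: 120 women at 2:1, so about 80 active and 40 placebo. Assumed: m women newly abnormal at Visit 2 and retested, of whom k are still abnormal. The printed Visit 3 cell is k/m; the same women over all N dosed are k/N; the ratio of the two is N/m. Active arm, half persisting:

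| New at Visit 2 | m of 80 | Printed k/m | k/80 | Ratio 80/m |
|---|---|---|---|---|
| 2.5% | 2 | 1/2 = 50% | 1.25% | 40 |
| 5% | 4 | 2/4 = 50% | 2.5% | 20 |
| 10% | 8 | 4/8 = 50% | 5% | 10 |
| 20% | 16 | 8/16 = 50% | 10% | 5 |

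The printed figure does not move while the rate of new abnormality varies eightfold. In the placebo arm the same rates give m = 1, 2, 4 and 8. With one woman retested, the cell can print only 0% or 100%.

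**2. Against true prevalence.** The ratios above compare two ways of expressing persistence. To compare with the real Visit 3 rate, 2,000,000 subjects were simulated with no drug effect: a standard normal marker with equal correlation between visits, abnormal above the upper 5% or 10% point, and retested if normal at Visit 1 and abnormal at Visit 2.

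| Correlation | True abnormal rate, every visit | Retested | Printed Visit 3 rate | Mean change from Visit 1, retested (SD) | Abnormal at Visit 3 and retested, of all |
|---|---|---|---|---|---|
| 0.5 | 5% | 3.8% | 18.9% | +0.224 | 0.7% |
| 0.5 | 10% | 6.7% | 24.7% | +0.292 | 1.7% |
| 0.7 | 5% | 3.0% | 26.9% | +0.249 | 0.8% |
| 0.7 | 10% | 5.3% | 31.6% | +0.292 | 1.7% |
| 0.9 | 5% | 1.8% | 36.6% | +0.198 | 0.7% |
| 0.9 | 10% | 3.1% | 39.8% | +0.215 | 1.2% |

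The printed percentage is 2.5 (24.7/10) to 7.3 (36.6/5) times the true rate. The mean change in all subjects is zero. The Visit 3 count errs the other way: it finds 0.7% to 1.7% of subjects when 5% or 10% are abnormal, because stable abnormalities and new late ones are not drawn.

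**3. The texts on which results are tabulated.** SAP 9.6 excludes unscheduled and repeated follow-up tests from tables and figures. The shells tabulate Visit 3 repeats. SAP 3.3.8 puts an unscheduled Visit 2 into all by-visit tables when the visit was missed. SAP 4.5 accepts several observations in a visit window and uses the one closest to schedule. No text says which rule prevails.

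**4. The outcome window.** Protocol 8.2.1 lets the investigator repeat any laboratory parameter at any time if an AE indicates it, and Protocol 7.4 includes a full safety panel at early termination. SAP 9.3.2 keeps protocol laboratory parameters out of the non-laboratory AE outcome. A transient worsening found only on such an unscheduled draw, in a woman who then attends Visit 2, therefore enters neither secondary outcome. How often this would happen cannot be estimated: the documents give no frequency for such draws.

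**The case against.** The restriction is disclosed. Visit 3 is flagged in Tables 90, 92 and 94, the retest rule is printed beneath, and each visit has its own N. The laboratory outcome ends at Visit 2, and SAP 9.6 plans no laboratory hypothesis test. Protocol 11.7.1.1 mentions logistic models of graded results, but names no visit, and SAP 9.6 does not carry them forward. All this stands and limits the point to descriptive tables. It does not make the Visit 3 cells comparable with their neighbours.

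A reader might infer that the Visit 3 column hides any difference between arms. The documents do not support that: Table 89 and the Visit 2 columns still show it, and the counts are printed. Equal Visit 3 percentages in an example follow from assuming equal persistence in both arms.

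A reader might also infer that misleading Visit 3 figures will certainly be printed. The exclusion sentence, read literally, would remove them. It can also be read as covering only draws outside the schedule, since Visit 3 labs are a conditional entry in the Schedule of Events. This is a conflict to reconcile, not proof either way. Nor can it be said that Figures 17-28 share the fault: they are not shown, and their titles do not establish that Visit 3 is plotted.

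On unscheduled draws, it would be too strong to say that results vanish. They stay in Listings 14-15, and results of Grade 1 or higher are in Tables 95-96. SAP 3.3.8 covers a missed Visit 2, and a worsening still present at Visit 2 is counted. Draws prompted by symptoms may also be more frequent in one arm, so adding them to the main count is debatable.

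**Conclusion.** The point holds for the Visit 3 percentages in Tables 90-93 and the Visit 3 mean, standard deviation, median and mean change in Table 94. They describe women selected on a bad Visit 2 result. Under no drug effect and the assumed inputs, the percentage overstates the true rate about 2.5 to 7.3 times, and the mean change is +0.20 to +0.29 SD when it should be zero. These sizes rest on assumed rates and correlations, a single cut-off on one side, and no modelling of already abnormal values that worsen. The direction follows from the retest rule itself. A repeated panel may bring in some normal parameters, but the women remain selected.

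The exclusion sentence in SAP 9.6 conflicts with the Visit 3 columns, and its relation to SAP 3.3.8 needs stating. The gap between the outcome window and the Visit 2 rule is real but narrow, limited to transient worsening, and cannot be sized. The Visit 3 problem does not affect Table 89.

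**What to change.** 1. Drop the Visit 3 percentages and summary statistics from Tables 90-94, and from any figure that plots Visit 3. Replace them with a by-arm table of what became of each Visit 2 laboratory AE: resolved, improved, unchanged, worse or not retested. Show counts and the number of women with a Visit 2 result.
2. Reword the exclusion in SAP 9.6 so that it agrees with SAP 3.3.8, the multiple-observation rule in SAP 4.5 and the shells. State where early-termination laboratory results are placed.
3. Keep Table 89 on scheduled Visit 2 values. Add a supplementary by-arm count of women with any graded worsening from baseline on any post-dose draw through Visit 2, including unscheduled and early-termination draws. Note beside it that symptom-triggered testing may differ between arms.

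The cost is SAP wording, revised shells and a little programming. No new data are needed, and the testing schedule does not change.
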